COSMOS-Mind will examine whether cocoa flavanols protect and even enhance cognitive function in older adults, an appropriate extension of the parent trial given the robust association between vascular and cognitive health.³⁴⁻³⁶ This association was the focus of a recent study of over 9,000 older adults drawn from the National Alzheimer's Coordinating Center: increased vascular risk, which included history of CVD and atrial fibrillation, predicted faster rates of cognitive decline in cognitively normal adults and in individuals with mild cognitive impairment (MCI).³⁶ Dietary consumption of cocoa flavanols may slow this decline through its beneficial effects on cerebral vasodilation, and thus on brain blood flow and perfusion, and angiogenesis.^{37,38} Epicatechin, the most common flavanol in cocoa, is rapidly absorbed, readily crosses the blood-brain barrier, can be detected in the brain,³⁹⁻⁴¹ and likely has accumulating physiological effects at high doses.^{40,42} This evidence for brain penetrance provides an important foundation for other cognition-enhancing mechanisms of flavanols at the neuronal level.^{43,44}

The effects of cocoa flavanols on cognition have been examined in animal studies for years, and consequently, putative underlying mechanisms related to endothelial function and pivotal signaling cascades for neuronal activity and viability are well described.³⁸ However, these mechanisms have not been fully explored in controlled clinical studies. Much of the support for a cognition-enhancing effect of flavanols in healthy older adults comes from observational studies, and a few small but promising controlled trials.^{45,46} In one large prospective study of 1640 older adults (≥ 65 yrs) followed for 10 years,⁴⁷ dietary intake of flavonoid-rich food (dark chocolate, wine, tea) was positively correlated with cognitive performance at baseline and over time in a dose-dependent manner. At the end of follow-up, participants in the lowest quartile for flavonoid

intake had lower Mini-Mental State Examination (MMSE) scores vs. those in the highest quartile. A favorable dose response of flavonoid intake on cognition was also reported in a large cross-sectional Norwegian study for a more extensive set of outcomes measuring attention and task-switching, verbal fluency, and spatial perception.⁴⁵ Regular flavonoid intake has also been linked to lower rates of prevalent cognitive impairment⁴⁸ and incident dementia.^{49,50}

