2. OBJECTIVES

COSMOS-Mind is an ancillary cognitive study to the large randomized double-blind, placebo-controlled COSMOS trial, coordinated through Brigham and Women's Hospital (BWH). The parent trial will test whether high-potency cocoa extract supplement administered alone or in combination with a standard multivitamin reduce risks of CVD and cancer in older adults. COSMOS-Mind will test whether 3 years of treatment with these supplements improves cognitive function and reduces risk of cognitive impairment, including AD and other forms of dementia.

Primary Aim

- Test whether random assignment to daily cocoa extract (capsule containing 750 mg/d flavanols, including 75 mg (-)-epicatechin, and 90 mg theobromine), compared to placebo, has favorable effects on a composite measure of cognitive function, over 3 years of follow-up in men and women who are 65 years and older

Secondary Aims

- Examine the effects of MTV use over 3 years of follow-up, relative to placebo, on a composite measure of cognitive function
- Assess treatment effects on incident MCI, and AD and other related dementias
- Compare intervention effects on cognitive domains of executive function and episodic memory

Tertiary Aims

- Examine consistency of treatment response for subgroups defined by age, sex, body mass index, baseline cognitive status, CVD, and type 2 diabetes
- Examine treatment effects on measures of sleep quality, depressive symptoms, and subjective memory concerns
- Share COSMOS-Mind data with the parent trial and its ancillary studies to expand its scientific impact

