6. STATISTICAL CONSIDERATIONS

The primary outcome for COSMOS-Mind is a composite measure of cognitive function that combines individual assessments of global cognitive function (TICSm), memory (SR), and executive function (OTMT, Verbal Fluency, NST, DOT). The composite provides a quantifiable measure of cognitive function across multiple domains and greater statistical power than individual measures even if the intervention effect varies moderately from one individual measure to another. It consolidates type 1 error into a single outcome. Secondary analyses, described below, will examine intervention effects on the constituent measures of the composite score.

The primary hypothesis is that random assignment to high potency cocoa flavanol extract compared to placebo will result in a mean difference over time in the global cognitive composite score. This hypothesis will be tested using 2-tailed type 1 error of 0.05. Inference will be based on the marginal effect estimated from a factorial study design, and a generalized linear model¹⁰¹ with the dependent variable consisting of all measured annual changes from baseline across years of follow-up on every participant, regardless of adherence (i.e. intent-to-treat). Data from the individual tests will be combined using a multivariate analysis of covariance (MANOVA) model within this framework with adjustment for sex, education, and age. In this model, all observed data can be included without special procedures for missing data, provided they are missing at random. The estimated differences will be combined using the ordinary least squares global test statistic.^{102,103} This statistic is the sum of the estimated differences of the individual tests divided by their standard errors, which produces a test statistic that is approximately normal with mean zero under the null hypothesis of no difference. Its standard error will be computed from the estimated correlation matrix of the treatment group differences. Cocoa flavanol effects will be examined by comparing cognitive response to active cocoa extract vs. its placebo, regardless of assignment to active MTV or its placebo.

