Secondary and tertiary aims. COSMOS-Mind will assess the relative effects of assignment to MTV using parallel analyses to those described above. The study will also assess whether effects of the two treatments interact on the primary outcome, adding a term to the model used in the primary hypothesis. If so, results from the primary marginal comparisons will be qualified. Individual cognitive test scores will be analyzed – paralleling the strategy used to test the primary hypothesis – in supporting analyses. The randomization effects on tertiary outcomes including cognitive complaints, sleep quality, and depressive symptoms will be assessed similarly to the intervention models used in the primary and secondary aims, and further tests will determine whether the treatments interact with respect to tertiary outcomes. Linear contrasts will be used to estimate treatment effects at 3 years. Tests of interactions will also assess the potential moderating effect of treatments among subgroups formed by age (<70 or ≥70 years old), sex, BMI (<25, 25-29, ≥30 kg/m²), baseline cognitive function (median split on TICSm), cognitive complaints (median split on CCI), depressive symptoms (median split on GDS-SF), hypertension, and diabetes; additionally, the preceding variables will also be assessed as continuous moderators of the intervention effects. The distribution of follow-up times to MCI and dementia will be assessed with proportional hazards regression. COSMOS-Mind will incorporate CVD and cancer events (from the parent trial) as change-points in the primary analyses to assess their impact on post-event cognitive trajectories. When needed, transformations (e.g. Box-Cox, rank, probit) will be used to improve the symmetry of residual distributions.

Interim Testing

No interim monitoring of treatment effects on cognitive outcomes is planned. COSMOS-Mind investigators will remain masked to treatment assignment until the parent trial is completed. Routine reports will assess retention, data completeness and quality, and cognitive trajectories over time. These reports will be sent to the COSMOS Coordinating Center for inclusion in DSMB reports.

Statistical Power

Longitudinal sequences of cognitive test scores from the WHIMS-ECHO study (N=2,878; 1-6 years of annual telephone assessments) were used to calculate the longitudinal covariance of measures in a simulation analysis. Loss-to-follow-up was set to accumulate at 5% per year, as per rates observed in WHIMS.¹⁰⁴ Based

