 - Create z-score by dividing the difference between individual scores and the raw cohort-wide baseline mean by the raw cohort-wide standard deviation

EF4. Attention/Working Memory 1

- Test: Number Span Forward and Backward
- Variables: dst_forwardtot; dst_backwardTot
- Approach
 - Sum digit forward and backwards scores (requires both to be non-missing)
 - Create z-scores by dividing the difference between individual scores and the raw cohort-wide baseline mean by the raw cohort-wide standard deviation

Composite Scores

General Cognitive Function

- Equal to GC1

Global Episodic Memory

- Average MEM1-MEM3, ignoring any missing data
- Create z-score by dividing the difference between individual scores and the raw cohort-wide baseline mean by the raw cohort-wide baseline standard deviation

Global Executive Function

- Average EF1-EF4, ignoring any missing data
- Create z-score by dividing the difference between individual scores and the raw cohort-wide baseline mean by the raw cohort-wide baseline standard deviation

Global Cognitive Composite

- Average z-scores from the following individual tests (note that this differs from averaging the three domain-specific z-scores and includes TICSm (Long) and Oral Trails A, which don't contribute to any of these):
 - TICSm total score
 - TICSm-Long to assess delayed memory
 - Story recall (immediate)
 - Story recall (delayed)

- Oral trails A (based on log transformation)
- Oral trails B (based on log transformation)
- Verbal fluency
- Category fluency
- Number span test (total of forward and backward)
- Create z-score by dividing the difference between individual scores and the raw cohort-wide baseline mean by the raw cohort-wide standard deviation

In the primary analyses, to follow intention-to-treat and use all available data to compare changes from baseline, we will include all cognitive assessments (baseline through Year 3) as dependent variables in general linear models (including data from participants with incomplete follow-up) and use linear contrasts to compare the average changes from baseline across follow-up between intervention groups: the difference between the average means at years 1, 2, and 3 and the baseline mean.

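### Do the CVD and cancer change-points in Protocol section 6 take the primary comparison away from intention-to-treat?

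*Protocol*

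**What the plan says.** The sentence is in Protocol section 6, in the paragraph that opens "Secondary and tertiary aims. COSMOS-Mind will assess the relative effects of assignment to MTV using parallel analyses to those described above". It reads "COSMOS-Mind will incorporate CVD and cancer events (from the parent trial) as change-points in the primary analyses" and ends with its purpose: "to assess their impact on post-event cognitive trajectories".

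The primary test is set out before that paragraph. Its dependent variable is "all measured annual changes from baseline across years of follow-up on every participant, regardless of adherence (i.e. intent-to-treat", and the model is fitted "with adjustment for sex, education, and age".

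The closing paragraph of the SAP describes the primary analysis again. It is designed "to follow intention-to-treat and use all available data to compare changes from baseline", and compares arms on the mean of Years 1 to 3 less the baseline mean. It mentions neither CVD and cancer events nor change-points.

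Two other places matter. Section 2 says the parent trial tests whether the supplements "reduce risks of CVD and cancer in older adults". Section 1 calls this cognitive study "an appropriate extension of the parent trial given the robust association between vascular and cognitive health".

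**The concern.** CVD and cancer events happen after randomisation and are endpoints of the parent trial. If cocoa extract prevents some of them, and events harm cognition, then prevented events are one route by which assignment improves cognition. A model with event change-points assigns post-event decline to the event terms, so the treatment coefficient leaves that route out. If frailty drives both events and cognitive decline, conditioning on events also makes the arms non-comparable within event status.

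Applied to the primary test, this would replace the randomised total effect with a conditional contrast, biased against any benefit that runs through prevented events. Because the sentence names the primary analyses, that reading is available.

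**Working it through.** **What the text specifies**

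| Place | Role | Event term? |
|---|---|---|
| Protocol section 6, primary hypothesis | Confirmatory test; sex, education and age as covariates | None |
| SAP, closing paragraph | Primary analysis; Years 1–3 mean less baseline | None |
| Protocol section 6, secondary and tertiary aims | Post-event trajectories | Change-points |

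The explicit covariate list in the Protocol is the strongest evidence. The SAP paragraph lists no covariates at all, so its silence on events counts for less. Its contrast is still a difference between arm means at the visits. With change-points in the model, that contrast would be undefined until someone stated the event status at which the means are taken, and the SAP states none.

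**The plan's own yardstick**

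The Protocol states more than 90% power for a sustained 0.10 SD effect with 2500 participants. The covariance behind it is not given, so it cannot be reproduced exactly. Assume 1250 per cocoa arm, unit SD and equal correlation r between visits. A baseline-adjusted mean of three visits has SD = √[(1+2r)/3 − r²]. At r = 0.4 with 15% loss (1062 per arm), SD = √(0.60 − 0.16) = 0.663 and power is 93.5%; it is higher for r up to 0.8. The claim is plausible and does not depend on the change-point sentence. Power of exactly 90% implies a standard error of 0.10/(1.96 + 1.28) = 0.031 SD.

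**Size if events did enter the primary model**

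The documents give no event rate, hazard ratio or post-event drop. Assumed: placebo three-year risk p of 5–15%, hazard ratio HR of 0.7–0.9, drop d of 0.1–0.5 SD.

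With λ = −ln(1−p)/3, the mediated effect removed from the Years 1–3 average is d × (1/3) Σ [exp(−λ·HR·t) − exp(−λt)] for t = 1, 2, 3.

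- Largest corner (p = 0.15, HR = 0.7, d = 0.5): λ = 0.0542. The three differences are 0.0155, 0.0296 and 0.0425, with mean 0.0292. Removed: 0.0292 × 0.5 = 0.0146 SD, or 14.6% of 0.10 SD.
- Middle (p = 0.10, HR = 0.8, d = 0.3): 0.0131 × 0.3 = 0.0039 SD, or 3.9%.
- Smallest corner (p = 0.05, HR = 0.9, d = 0.1): 0.0033 × 0.1 = 0.0003 SD, or 0.3%.

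A simulation of 1,000,000 participants per scenario added a direct effect of 0.10 SD and a shared frailty (log-hazard 0.7 per SD of frailty; cognition lower by 0.3 SD per SD at year 3). It compared the intention-to-treat difference with the treatment coefficient after change-points were added:

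| HR | p | d | Intention-to-treat | With change-points | Difference |
|---|---|---|---|---|---|
| 1.0 | 0.15 | 0.5 | 0.0999 | 0.0997 | 0.0002 |
| 0.9 | 0.05 | 0.1 | 0.0992 | 0.0984 | 0.0008 |
| 0.8 | 0.15 | 0.5 | 0.1098 | 0.0973 | 0.0126 |
| 0.7 | 0.15 | 0.5 | 0.1154 | 0.0970 | 0.0184 |

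At HR = 1 every difference was within 0.0004. The largest, 0.0184, is 0.0184/0.031 = 0.6 of a standard error.

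**Could the sign reverse?**

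In a second simulation (1.5 million participants, benefit only through CVD), total effects were 0.0002 to 0.0079 SD and adjusted coefficients −0.0007 to −0.0012. If the outcome SD is about 1, the Monte Carlo standard error is √(4/1,500,000) = 0.0016. The negative values cannot be told from zero, so no reversal is shown.

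**The case for a change.** The best opposing case rests on the words. The sentence names the primary analyses, and the SAP uses that label for its confirmatory analysis. Elsewhere in the same Protocol paragraph add-ons are marked as such: the treatment interaction is an extra term in the primary-hypothesis model, and the individual tests are supporting analyses. The change-point sentence has no such marker, and the SAP neither repeats nor withdraws it. Nor does an intention-to-treat label by itself exclude post-randomisation covariates. One clarifying sentence would cost almost nothing.

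Two parts of this stand. The wording is loose, and a treatment coefficient from a model with event change-points should not be read as the total effect of assignment.

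The inference to the primary test does not stand. The interaction example shows the authors reusing the primary model for secondary questions, which is the natural reading here too. The purpose clause concerns what happens to cognition after an event, not the cocoa effect. The Protocol's covariate list for the primary test is explicit and contains baseline variables only. The clarifying sentence would record what those passages already specify.

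**Conclusion.** No change is needed. The documents do not show that the primary contrast is conditioned on CVD or cancer events. Its two specifications contain no event term, and the placement and purpose of the disputed sentence mark a descriptive secondary analysis built on the primary model. What remains is a slip of wording that analysts can resolve from the surrounding text.

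The methodological principle is right: such a model does not estimate the total effect. If it were misapplied, the shift would be about zero without a treatment effect on events, and roughly 0.001 to 0.018 SD with hazard ratios of 0.7 to 0.9. These sizes rest wholly on the assumed event risks, hazard ratios, post-event drops and frailty, and the yardstick on an assumed 1:1 cocoa margin. No planned sample size, error rate or stated power depends on the point.

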7. CONFIDENTIALITY

Appropriate measures will be in place to protect against risk of disclosing confidential information. The data will be collected for research purposes only. All paper records of the telephone assessments will be stored in locked cabinets in locked rooms, accessible only to the COSMOS-Mind investigators and staff. Participants will be assigned a unique study identifier code on all study questionnaires and forms. All electronic data – including the master list pairing participants' names and codes, recordings of telephone assessments, personal health information, and study outcomes – will be stored in password-protected files on a secure network in a secured area. This network is protected with frequently-updated anti-virus and anti-Trojan software, limited file sharing and file permissions to approved users only, and automated monitoring of access attempts; these procedures have successfully maintained security for many multicenter clinical trials coordinated by Wake Forest. COSMOS-Mind and COSMOS will develop data transfer procedures and protocols using password protection and encryption, to permit seamless and secure exchange of information. Safety monitoring will be provided by the DSMB of the parent trial.

8. SAFETY MANAGEMENT

Potential Risks

The COSMOS-Mind procedures pose minimal risk to participants, which are primarily related to possible emotional discomfort related to cognitive testing and answering questions relating to self-perceptions of memory and mood. Participants could experience distress when learning that they may have a significant cognitive impairment, following adjudication by dementia experts. COSMOS-Mind will only be contacting those with suspected dementia (i.e. not those with MCI), thus the letter will likely support preexisting suspicions regarding the participant's cognitive status.

Cognitive and Mood Assessment

Examiners will be extensively trained to identify and appropriately respond to discomfort associated with cognitive testing, or questions about self-perceptions of memory or mood, including discontinuing the assessment, if necessary. A study clinician experienced in the assessment and treatment of geriatric psychiatric disorders ([name]) will contact participants who express suicidal ideation in the context of the mood assessment. Similar telephone-based testing protocols have been extensively used in other studies (e.g., WHIMS-ECHO, WHIMS-Y) with relatively fewer reports of participant discomfort in telephone-based versus face-to-face assessments.

Disclosure Regarding Suspected Cognitive Impairment

Participants with an adjudicated classification of probable dementia will receive a letter to alert them that the COSMOS-Mind test results suggest a significant cognitive impairment and to advise them to follow-up with their personal physician. A Release of Information form will be included with the letter with instructions to sign and return this form to the COSMOS-Mind team to request a summary of the results be sent to his/her primary care provider. The adjudication panel of dementia experts ([name], [name], [name]) will be available to these

participants by telephone upon request. This disclosure protocol, developed for WHIMS has identified over 400 cases of probable dementia since WHIMS was initiated.

A 'Cognitive Alert' will be generated when an informant endorses items on the DQ that indicate impaired functional status (i.e.: 'yes' to any of Q1-Q6 ~AND~ 'yes' to any of Q14-16, Q18; ~OR~ answer to Q10 indicates diagnosis of dementia or AD). When this occurs, members of the adjudication team ([name], [name]) will review the available test results to assess whether a classification of dementia is warranted. If so, the participant will receive the alert letter informing them of a possible cognitive impairment and to encourage follow-up.

Protection against Risk

The principles listed in the current edition of the Declaration of Helsinki will be implemented. Appropriate measures will be in place to protect against the risk of disclosing confidential information. The data will be collected for research purposes only. All paper records of the telephone assessment will be stored in locked cabinets in locked rooms, accessible only to the COSMOS-Mind investigators and staff. Participants will be assigned a unique study identifier code on all study questionnaires and forms. All electronic data – including the master list pairing participants' names and codes, recordings of telephone assessments, personal health information, and study outcomes – will be stored in password-protected files on a secure network in a secured area. This network is protected with frequently updated anti-virus and anti-Trojan software, limited file sharing and file permissions to approved users only, and automated monitoring of access attempts. These procedures have successfully maintained security for many multicenter clinical trials. COSMOS-Mind will work with the COSMOS team at BWH to develop data transfer procedures and protocols using password protection and encryption, to permit seamless and secure exchange of information. Safety monitoring will be provided by the DSMB of the parent trial.

Potential Benefits of the Proposed Research to Human Subjects and Others

There is an urgent need to identify effective strategies to slow or prevent age-related cognitive decline. Although there may be no direct benefit to the participant for taking part in the study, COSMOS-Mind will provide a time- and cost-efficient assessment of whether a promising, safe, and widely translatable intervention can preserve cognitive function in older adults.

Importance of the Knowledge to be Gained

COSMOS-Mind will expand the scientific scope of the parent trial to include data about potential cognitive effects of the treatments that may reduce risk of cardiovascular disease and cancer in older adults. This intervention is inexpensive, easily accessible, and safe. If daily use of high-potency cocoa flavanol extract, with or without a multivitamin, attenuate age-related cognitive decline and impairment, this research could have significant implications for standard of care to protect and preserve cognitive function in a fast-growing aging population in the US and worldwide.

Data and Safety Monitoring Plan

As an ancillary study to COSMOS, COSMOS-Mind will adhere to the reporting procedures to be established by the COSMOS DSMB. The COSMOS DSMB is expected to include representatives from the established VITAL and WHI DSMBs, together with additional experts in epidemiology, biostatistics, and other relevant clinical areas, including CVD and cancer. The possibility that an adverse event is reported during the telephone assessment is small; however, should this occur, staff will notify the COSMOS team to initiate their safety protocols.

